² For each patient, the main trial and study partner consents must be obtained. Optional consents include bio banking and speech analysis.

³ Urine drug screen, pregnancy test and safety labs may be performed more frequently based on investigator discretion or if required locally. Pregnancy tests are required for women of child-bearing potential only. If urine (dipstick) pregnancy test is positive, a serum sample must be collected.

18 Sep 2023

Proprietary confidential information © 2023 Boehringer Ingelheim International GmbH or one or more of its affiliated companies

⁴ Randomized treatment period:

. For further details refer to Section 5.3 and Appendix 10.1.

Clinical Trial Protocol

- One sample for DNA bio banking will be taken, preferably at Visit 2. However, DNA sample collection may occur at a later visit as long as the informed consent for bio banking remains valid. At visit 2, plasma and serum bio banking samples are to be collected prior to IMP intake. Plasma and serum bio banking samples are to be collected at (e)EoT.
- ⁶ Speech sample collection may not be available in all countries at initiation and therefore may be implemented as soon as it is available and approved by regulatory authorities and ethic committees in participating countries.
- At visit 2, the MINI does not need to be repeated however the results from visit 1 should be confirmed and documented in the source documents.
- ⁸ AiCure training may be repeated as needed.
- ⁹ At visit 2, all assessments must be completed prior to IMP intake.
- ¹⁰ At early EOT (eEOT), PRECIS should not be administered immediately after MCCB, to avoid bias.
- ¹¹ For AEs that suggest potential study medication abuse refer to Section 5.2.6.5 and after the patient stops taking the study medication, refer to Section 5.2.6.6 for monitoring withdrawal AEs after stopping of study treatment.
- ¹² Details on alcohol, nicotine and caffeine use will be collected.
- ¹³
 ¹⁴ For patients not rolling over to the extension study: after the individual patient's end of the study, the investigator should report only any cancers of new histology

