4.1.4 Drug assignment and administration of doses for each patient

Dispensing of medication kits for the double-blind treatment period will begin at Visit 2. Throughout the treatment period, 2 trial medication kits will be provided at each visit. Medication assignment will be provided through IRT. The assigned medication kit numbers must be entered in the eCRF, and the corresponding medication kits must be given to the patient. The duration of treatment is 26 weeks. At each of the visits, patients will receive supplies for a total of 4 weeks.

The first dose of study medication will be taken at the end of Visit 2 under supervision of the investigator or delegated site staff, after all Visit 2 assessments have been completed. In case the Visit 2 is split into 2 sequential days, the first dose of study medication should be taken on the second day of the split visit, after all Visit 2 assessments have been completed.

Throughout the study, patients should be instructed to take 1 tablet orally with water and with or without food after waking up. If a dose is missed by more than 12 hours, that dose should be skipped and the next dose should be taken as scheduled.

Patients should be instructed **not** to take their study medication at home on the day of the clinic visit as patients will be dosed at the site. Dosing should occur approximately 24 hours after the drug administration from the preceding day.

Page 44 of 112

Proprietary confidential information © 2023 Boehringer Ingelheim International GmbH or one or more of its affiliated companies

The last dose of study medication should be taken on the day before the EoT Visit. In case the EoT Visit is split into 2 sequential days, the last dose of study medication should be taken on the day before the first day of the split visit.

On longer visit days the dosing may occur in the afternoon.

A dose reduction of Iclepertin is not possible.

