#### 6.7 BASELINE, TIME WINDOWS AND CALCULATED VISITS

In general, baseline values are the measurements taken prior to the first administration of trial medication. For assessments of efficacy, and C-SSRS, baseline will be defined as the last available assessment performed at or before randomization (Visit 2), and no later than the day of the first administration of study medication. Assessments done at Visit 1 or Visit 1a can be used as baseline if Visit 2 assessment is not planned, not available, or invalid.

For MCCB, only the assessment performed at randomization (Visit 2), and no later than the day of the first administration of study medication will be used as the baseline. If no valid assessment is available at Visit 2 then baseline value will be missing; assessments performed at Visits 1 and 1a will not be used as baseline.

Tables in this section define the analysis visits and windows which will be used for the analyses of efficacy and safety endpoints. Actual study day will be calculated starting with the date of first administration of trial treatment as Day 1. Unscheduled assessments will be mapped to the analysis visits together with the scheduled assessments.

Inclusion of an assessment into mapping consideration will depend on its on-/off-treatment status and per specific estimand (i.e., off-treatment data will be included into mapping consideration only when the associated ICE is handled under the treatment policy approach). If more than one assessment falls into the same analysis visit window, the assessment

performed closest to the planned day will be selected for analyses. In case of a tie, the later assessment will be used.

Table 6.7: 1 Analysis visit windows for MCCB, VRFCAT, SCoRS,

Analysis Visit	Nominal Week	Planned Day	Actual Day Window
Baseline		1	≤1
Visit 6	Week 12	85	2 – 126
Visit 11	Week 26	183	≥127

Table 6.7: 2 Analysis visit windows for PRECIS,

Analysis Visit	Nominal Week	Planned Day	Actual Day Window
Baseline		1	≤1
Visit 7	Week 15	106	2 – 126
Visit 10	Week 24	169	≥127

Table 6.7: 3 Analysis visit windows for Tower of London,

Analysis Visit	Nominal Week	Planned Day	Actual Day Window
Baseline		1	≤1
Visit 11	Week 26	183	≥2
(for Tower of London,			

[figure not shown]

Table 6.7: 7 Analysis visit windows for clinical laboratory evaluations (on-treatment period)

Analysis Visit	Nominal Week	Planned Day	Actual Day Window
Baseline		1	≤1
Visit 2	Week 0 (post-baseline)	1	2 – 35
Visit 4	Week 6	43	36 – 77

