Visit 6	Week 12	85	78 – 119
Visit 8	Week 18	127	120 – 140
Visit 9	Week 21	148	141 – 161
Visit 10	Week 24	169	162 – 175
Visit 11	Week 26	183	≥176

All post-baseline actual day windows will be curtained at the end of residual period if earlier than the specified upper bound in the table.

Table 6.7: 8 Analysis visit windows for weight and vital signs (on-treatment period)

Analysis Visit	Nominal Week	Planned Day	Actual Day Window
Baseline		1	≤1
Visit 2	Week 0 (post-baseline)	1	2 – 56
Visit 5	Week 9	64	57 – 119
Visit 8	Week 18	127	120–175
Visit 11	Week 26	183	≥176

All post-baseline actual day windows will be curtained at the end of residual period if earlier than the specified upper bound in the table.

[figure not shown]
Table 6.7: 9 Analysis visit windows for clinical laboratory evaluations, weight, and vital signs (post-treatment period)

Analysis Visit	Nominal Week	Planned Day	Actual Day Window (days after last dose)
Follow-up 2	14 days post-treatment	EOT + 14 days	13 – 19
Follow-up 4	21 days post-treatment	EOT + 21 days	20 – 26
Follow-up 6	28 days post-treatment	EOT + 28 days	>27

This analysis visit windows only apply to the post-treatment period defined in Table 6.1: 2

Table 6.7: 10 Analysis visit windows for PWC-20

Analysis Visit	Nominal Week	Planned Day	Actual Day Window (days after last dose)
Last value on treatment			<7
Follow-up 1	7 days post-treatment	EOT + 7 days	7 – 13
Follow-up 2	14 days post-treatment	EOT + 14 days	14 – 16
Follow-up 3	17 days post-treatment	EOT + 17 days	17 – 20
Follow-up 4	21 days post-treatment	EOT + 21 days	21 – 23
Follow-up 5	24 days post-treatment	EOT + 24 days	24 – 27
Follow-up 6	28 days post-treatment	EOT + 28 days	28 – 41
Post safety follow up			≥42

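### SAP Tables 6.7: 7 and 6.7: 8 display on-treatment laboratory values from Days 2-35 and weight/vital-sign values from Days 2-56 at Visit 2 / Week 0, planned Day 1, a visit with no post-dose measurement

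*SAP*

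**What the plan says.** SAP section 6.7 sets the day origin: "Actual study day will be calculated starting with the date of first administration of trial treatment as Day 1". Tables 6.7: 7 (laboratory) and 6.7: 8 (weight, vital signs) each have a Baseline row for Day 1 or earlier. Each then has a separate Visit 2 row labelled "Week 0 (post-baseline". Its entries, in the order nominal week, planned day, window, are:

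- laboratory: "Week 0 (post-baseline) 1 2 – 35"
- weight and vital signs: "Week 0 (post-baseline) 1 2 – 56"

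The next rows are "Visit 4 Week 6 43 36 – 77" and "Visit 5 Week 9 64 57 – 119". Post-baseline windows are cut at the end of the residual effect period, which is 12 days after the last dose. Unscheduled values are mapped together with scheduled ones. If several values fall in one window, the one nearest the planned day is used.

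Flow Chart footnote 9 of the protocol states: "At visit 2, all assessments must be completed prior to IMP intake". Section 4.1.4 agrees: "The first dose of study medication will be taken at the end of Visit 2". If Visit 2 is split over two days, the first dose is taken on the second day, after all assessments. The Flow Chart schedules the next laboratory sample at Visit 4 (Day 43 ±3) and the next weight and vital signs at Visit 5 (Day 64 ±3). The eEOT visit, which includes all three, is due within 7 days of stopping the drug.

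**The concern.** A Visit 2 measurement is by design a baseline measurement. A post-baseline Visit 2 row therefore has no scheduled content, yet it carries a nominal week and a planned day that state when its contents were measured. Values taken after as much as five weeks (laboratory) or eight weeks (weight, vital signs) of dosing would be read as Week 0 values.

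This matters most for haemoglobin. The protocol treats its decrease as a risk (Table 1.4.2:1: mean change -3.3 g/L on 10 mg against -0.5 g/L on placebo in phase II) and gives it its own alerts. A reader following haemoglobin over time needs to know how long a patient had been exposed when the value was taken. For weight and vital signs, the SAP specifies no summary that would make up for the wrong time label.

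**Working it through.** **1. The bounds are deliberate.** Every window in both tables opens 7 days before its planned day and closes 8 days before the next planned day:

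- laboratory, Visit 2 row: 43 - 8 = 35; Visit 4 opens at 43 - 7 = 36
- weight/vital signs, Visit 2 row: 64 - 8 = 56; Visit 5 opens at 64 - 7 = 57

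Days 35 and 56 are reproduced, so neither is a misprint.

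**2. What can fall in the row.**

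- Visit 2 itself: no. All assessments precede the first dose, so they belong to Baseline.
- Visit 4 laboratory: no. The earliest day is 43 - 3 = 40, after Day 35.
- Visit 5 weight/vital signs: no. The earliest day is 64 - 3 = 61, after Day 56.
- Follow-up visit 2 of an early stopper: no. It comes at the earliest 14 - 1 = 13 days after eEOT, beyond the 12-day residual period.
- eEOT values: yes. An on-time eEOT is 0-7 days after the last dose, and 7 < 12, so it counts as on-treatment.
- Unscheduled values: yes, including those of continuing patients. Protocol 5.2.3 allows repeat tests at any time. Under 5.2.6.4 a haemoglobin alert calls for both haematology panels at the next visit. After an alert at Visit 2, that is Visit 3, Day 22, inside Days 2-35.

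**3. How far the label is from the measurement.**

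| Value | Days from planned Day 1 | Days to next planned visit |
|---|---|---|
| Laboratory, Day 35 | 35 - 1 = 34 (4.9 weeks) | 43 - 35 = 8 |
| Weight/vital signs, Day 56 | 56 - 1 = 55 (7.9 weeks) | 64 - 56 = 8 |

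**4. Which value is kept.** With planned Day 1, the closest value is always the earliest. A patient with an unscheduled sample on Day 10 (distance 9) and an eEOT sample on Day 35 (distance 34) would be represented by Day 10, and the longer-exposed value would drop out of the by-visit table.

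**5. How many patients (illustration).** Inputs from protocol 7.5: 586 randomised, 30-40% stopping early. Assumptions: stopping spread evenly over 182 days, and everyone attends eEOT. The documents give neither stopping times nor eEOT attendance. For a window ending on Day D and an eEOT lag of L days, the count is 586 × p × (D - L)/182.

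| Window | Lag 0 days | Lag 7 days |
|---|---|---|
| Laboratory, D = 35 | p = 0.30: 34; p = 0.40: 45 | p = 0.30: 27; p = 0.40: 36 |
| Weight/vital signs, D = 56 | p = 0.30: 54; p = 0.40: 72 | p = 0.30: 47; p = 0.40: 63 |

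The ranges are 27-45 and 47-72. Lower attendance reduces them in proportion. A constant stopping hazard h = -ln(1 - p)/182 puts more stops early: 586 × (1 - exp(-34h)) = 38-53 stop by Day 35, and 586 × (1 - exp(-55h)) = 60-84 by Day 56, before any eEOT lag.

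**The case against.** The strongest reply is that this is one consistent windowing rule, and that other rows stretch as far. Day 77 is called Week 6 although it is 34 days after Day 43, and in Table 6.7: 8 Day 119 is called Week 9 although it is 55 days after Day 64. That is true, and it is why the bounds should stay. It does not rescue the label. In the later rows a scheduled value normally lies near the planned day and wins selection. The Week 0 row has no scheduled value, so what it displays is always off its stated time.

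Four stronger readings are tempting, and the documents do not support them:

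- *The windows remove early stoppers from Week 6 and Week 9.* Mostly this is the on-treatment cut-off. A patient last dosed by Day 27 is on-treatment only to 27 + 12 = Day 39, before the earliest Visit 4 (Day 40). One last dosed by Day 48 is on-treatment only to Day 60, before the earliest Visit 5 (Day 61). Such a patient cannot supply an on-treatment value at that visit, whatever the row is called.
- *The haemoglobin time course is materially distorted.* The row is marked post-baseline and kept apart from Baseline, and N is part of the end-of-text summaries, so a sparse row would be visible. Table 1.4.2:1 places the maximum decrease for other drugs of the class after 4 months, where the windows are unaffected. Shift tables to minimum, maximum or last on-treatment value (SAP 7.8.2) do not use the visit label.
- *The row would consist almost entirely of early stoppers.* Repeat and alert-driven samples from continuing patients also enter, in unknown number.
- *The first windows should be split at midpoints.* Moving the start of Week 6 to Day 23, or of Week 9 to Day 33, would mix stoppers' shorter-exposure values into the scheduled-visit means and break the tables' own rule.

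**Conclusion.** The point holds as a labelling and selection fault in descriptive safety tables. The row assigns Week 0 and planned Day 1 to values that can only be eEOT or unscheduled measurements, up to 34 days (laboratory) or 55 days (weight, vital signs) after first dose, and it prefers the earliest of them. These facts follow from the documents without any assumption.

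The headcounts of about 27-45 and 47-72 patients do rest on assumptions: 30-40% stopping, even timing, full eEOT attendance and a lag of 0-7 days. They show only that the row need not be empty.

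Baseline values, change from baseline, every hypothesis test and the laboratory shift tables are unaffected. The point is minor, but a correction costs almost nothing. It is worth most for weight and vital signs, where SAP 7.8.3 plans descriptive statistics only and names no shift table as a backup.

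**What to change.** In both tables, keep the bounds and replace the Visit 2 / Week 0 label and planned Day 1 with a row named by actual days and no nominal week:

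- Table 6.7: 7: *Early on-treatment, unscheduled/eEOT, Day 2-35*
- Table 6.7: 8: *Early on-treatment, unscheduled/eEOT, Day 2-56*

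Add one sentence to SAP 6.7: for this row, the last on-treatment value in the window is selected, not the one closest to a planned day. Leave the Visit 4 and Visit 5 windows as they are.

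The SAP already has models for this. Table 6.7: 10 uses rows without a nominal week, and efficacy Tables 6.7: 1 to 6.7: 3 have no post-baseline Week 0 row. The cost is two table rows, one sentence and the matching programming. Data collection does not change.

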Safety Laboratory tests ³	X		X		X		X		X	X^H	X	X	X		(X)		X		X	
PK Sample ⁴				X	X		X		X			X	X		X					
Bio-banking (optional) ⁵			X									X	X							
Speech sampling (optional) ⁶		X				X					X									
M.I.N.I. ⁷	X		X																	
In-/exclusion criteria	X		X																	
Randomization			X																	
AiCure training ⁸	X	(X)	X																	
AiCure review		X	X	X	X	X	X	X	X	X	X	X	X							
Contact IRT	X		X	X	X	X	X	X	X	X	X	X	X						X	
Duplicate patient check	X																			
(re)Dispense & administer trial drug at site ⁹			X	X	X	X	X	X	X	X	X									
IMP Compliance check				X	X	X	X	X	X	X	X	X	X							
Termination of trial drug												X	X							
MCCB	X		X				X					X	X							
VRFCAT	X		X				X					X	X							
PCRS & SCoRS ²⁰	X		X				X					X	X							
Tower of London	X		X									X	X							
		X	X				X				X	X	X		X		X		X	

Page 7 of 112

Proprietary confidential information © 2023 Boehringer Ingelheim International GmbH or one or more of its affiliated companies

FLOW CHART (con't)

Trial Periods and Procedures	Screening	g Period ¹				F	Rando	mized	Treat	ment l	Period	l			Sat	fety Follo	w-up Perio	od ¹⁸		End of Study
Visit	1	1a	2	3	4	5	6	7	8	9	10	EOT/11 ¹⁶	eEOT ¹⁷	Follow- up 1	Follow- up 2	Follow- up 3	Follow- up 4	Follow- up 5	Follow- up 6 ¹⁹	EOS
Weeks	Scree	ning	0	3	6	9	12	15	18	21	24	26	NA							
Days from first randomized treatment	-35 1		1	22	43	64	85	106	127	148	169	183	NA	EOT or eEOT + 7	EOT or eEOT +14	EOT or eEOT +17	EOT or eEOT +21	EOT or eEOT +24	EOT or eEOT + 28	
Clinic (on-site) visit	X	X	X	X	X	X	X	X	X	X	X	X	X		X		X		X	
Visit time window (days)	-35 to -28	-14 to -7	N/A	±3	±3	±3	±3	±3	±3	±3	±3	±3	NA	±1	±1	±1	±1	±1	+7	
PRECIS ¹⁰		X						X			X		X							
Adverse events ¹¹	X	X	X	X	X	X	X	X	X	X	X	X	X	X	X	X	X	X	X	
		X										X	X							
Concomitant therapy	X	X	X	X	X	X	X	X	X	X	X	X	X	X	X	X	X	X	X	
Substance use ¹²	X		X				X					X	X							
C-SSRS ²¹	X	X	X	X	X	X	X	X	X	X	X	X	X	X	X	X	X	X	X	
SAS/AIMS/BARS		X			X			X			X	X	X							
Physician withdrawal checklist ¹³											X		X	X	X	X	X	X	X	
Patient Participation Completion 14																				X
Duration in hours ¹⁵	7	3	6.5	1	2	2	4.5	2	2.5	1	3	6.5	7	0.5	2	0.5	3	0.5	3	

(X) Optional assessments at discretion of investigator

¹The screening period may take up to 35 days with 2 visits. At the second screening visit, urine drug screen may be repeated at discretion of investigators (X), if needed.

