3.2 DISCUSSION OF TRIAL DESIGN, INCLUDING THE CHOICE OF CONTROL GROUP(S)

A parallel group design is appropriate to detect the effects of Iclepertin 10 mg compared to placebo on cognitive impairment in clinically stable patients with schizophrenia. The primary analysis of efficacy is planned after 26 weeks of treatment. Elimination of Iclepertin takes approximately 12 days, therefore 28 days is considered sufficient to detect any unexpected late onset AEs, to evaluate the pharmacodynamic effect of Iclepertin after discontinuation and to allow for assessment of reversibility of any unexpected side-effects. Refer to section 5.2.6.4 for follow up of Hb related issues.

Details of the statistical approach and sample size justification are given in Section 7.

There is currently no approved medication indicated for treatment of CIAS and therefore, a placebo control group is being used in this study. It should be noted that all patients, including those randomized to the placebo group, are permitted to remain on other antipsychotic and psychotropic medications, within the eligibility criteria. The risk to the control group is discussed in Table 1.4.2:1.

A DMC, independent from the Sponsor, will be established to review the safety data at regular intervals, and to recommend to the Sponsor whether to continue, modify, or stop the trial based on periodic safety monitoring. The tasks and responsibilities of the DMC members will be detailed in the DMC charter.

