5.2.6.4 Haemoglobin and anaemia

To reduce bias on efficacy assessments, starting at visit 2 until the end of trial, **Haematology Panel A parameters** (refer table 5.2.3:1) will be blinded to the site and to the sponsor.

Clinical Trial Protocol

Page 64 of 112

Proprietary confidential information © 2023 Boehringer Ingelheim International GmbH or one or more of its affiliated companies

Sites will be alerted if the following occurs:

- Alert 1: Hb decrease > 20 g/L (2 g/dL) compared to baseline value
- Alert 2: The Hb value is below the normal reference range
- Alert 3: Hb value fulfils the criteria to withdraw the treatment (refer to section 3.3.4)

An independent third party will review both **haematology panels** throughout the trial. In addition, the independent DMC will review unblinded safety data on a regular basis throughout the study.

Scenarios and Actions:

Alert 1:

- Patients may continue on the study medication.
- Both haematology panels should be performed at the next visit (or earlier, per investigator's judgement). Both haematology panels should be repeated at subsequent visits until alerts are no longer triggered or once the end of study has been reached.

Alert 2:

- Patients may continue on the study medication.
- Both haematology panels should be performed at the next visit (or earlier, per investigator's judgement). Both haematology panels should be repeated at subsequent visits until alerts are no longer triggered or once the end of study has been reached.
- The investigator should further evaluate the patient status and report the AE "anaemia" based on investigator's clinical judgment. Once Alert 2 is no longer trigged, the investigator may evaluate whether or not the AE "Anaemia" is resolved.

For Alert 1 and/or 2, patients can be rolled over to the extension study. Details on monitoring of an ongoing adverse event "Anaemia" in the extension study will be provided in 1346-0014 study protocol [c33088336].

Alert 3:

- **Stop study medication.** Refer to section 3.3.4.2.
- Report as an AE "Anaemia"
- Both haematology panels should be performed at the next visit (or earlier, per investigator's judgement). Both haematology panels should be repeated at subsequent visits until alerts are no longer triggered or once the end of study has been reached.
- Patient should be referred to a specialist for further management.
- Patients are not eligible for the extension trial.

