### 7.8.2 Laboratory data

The analyses of laboratory data will be descriptive in nature and will follow BI standards (4).

Descriptive statistics for laboratory values will be displayed using the converted values in standard unit for data analyzed by the central laboratory. Shift tables of change in laboratory measurements between baseline and minimum, maximum or last value on treatment will be presented.

Page 41 of 54 c45059945-01

Proprietary confidential information © 2024 Boehringer Ingelheim International GmbH or one or more of its affiliated companies

Data in the post-treatment period will also be summarized.

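### Laboratory tests at Follow-up 2 are optional, and haematology there is more likely after a haemoglobin alert, yet the SAP summarises them as an ordinary visit, so the Follow-up 2 haemoglobin mean can be biased low

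*SAP*

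**What the plan says.** - **Protocol, Flow Chart.** The row "Safety Laboratory tests ³" carries X at EOT, eEOT, Follow-up 4 and Follow-up 6, a bracketed (X) at Follow-up 2, and nothing at Follow-up 1, 3 and 5. The key explains the bracketed mark: "X) Optional assessments at discretion of investigator". Weight and vital signs carry a plain X at Follow-up 2.
- **Protocol 5.2.6.4.** An alert goes to the site if haemoglobin falls by more than 20 g/L from baseline, lies below the reference range, or meets the withdrawal criteria. For each alert: "Both haematology panels should be performed at the next visit (or earlier, per investigator's judgement". Then: "Both haematology panels should be repeated at subsequent visits until alerts are no longer triggered or once the end of study has been reached".
- **Protocol 4.1.5.1.** Haemoglobin parameters are blinded to the site from Visit 2, so a central haemoglobin value can prompt a test only through an alert.
- **Protocol 6.2.4.** Follow-up 1, 3 and 5 are by telephone.
- **SAP 6.7.** The table is titled "Table 6.7: 9 Analysis visit windows for clinical laboratory evaluations, weight, and vital signs (post-treatment period". Days after last dose: Follow-up 2 is 13–19, Follow-up 4 is 20–26, Follow-up 6 is beyond 27. One table serves laboratory data, weight and vital signs, and unscheduled tests are mapped in as well.
- **SAP 7.8.2.** Laboratory analyses are descriptive, and "Data in the post-treatment period will also be summarized". The available text has no footnote, restriction or paired comparison for the optional visit.
- **Protocol 3.2.** The 28-day follow-up is meant, among other things, "to allow for assessment of reversibility of any unexpected side-effects".

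**The concern.** Haemoglobin decrease is a listed drug risk (protocol Table 1.4.2:1), and the first laboratory row after the residual effect period is Follow-up 2. At EOT, Follow-up 4 and Follow-up 6 every attending patient should have a sample. At Follow-up 2 the sample consists of patients whom the site chose to test, and a haemoglobin alert is one reason to test. Selection therefore depends on the variable being summarised.

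Read down the visits, such a table compares nearly everyone, then a subset that leans towards low haemoglobin, then nearly everyone again. A reader could see a further fall after stopping drug, followed by recovery, when nothing happened. Or a real early recovery could be masked. The displayed N shows that the Follow-up 2 sample is smaller. It does not show that the sample was selected on haemoglobin.

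**Working it through.** The plan states no figure on this point, so there is none to reproduce.

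**1. Do Follow-up 2 tests land in the row?** For completers the last dose is the day before EOT (protocol 4.1.4). Follow-up 2 is EOT + 14 ± 1, so it falls on days 14–16 after last dose, past the 12-day residual effect period and inside 13–19. Follow-up 4 falls on days 21–23 and Follow-up 6 (window +7) on days 29–36. After an alert at EOT, the next on-site visit is Follow-up 2.

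**2. Size of the selection effect.** Let *a* be the share of patients with an alert at EOT, *q* the share of the others who are tested at Follow-up 2 (assumed a random fraction), and D(0) the shortfall of the alerted patients' mean below the all-patient mean. Then

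D(q) = D(0) × a(1 − q) / [a + (1 − a)q].

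From the documents: the alert rules; entry haemoglobin not below the lower limit; phase II mean changes of −3.3 g/L (10 mg) and −0.5 g/L (placebo), a difference of 2.8 g/L. Assumed, because the documents do not give them: 65% men; means 150/136 g/L and lower limits 130/118 g/L by sex; between-patient SD 10; visit-to-visit SD of change 5; SD of individual drug-period change 5; no true change after EOT; and *q* itself.

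Simulating the iclepertin arm gives a = 6.9% and D(0) = 18.0 g/L in absolute haemoglobin, or 5.6 g/L in change from baseline. The multiplier is
- q = 10%: 0.069 × 0.9 / (0.069 + 0.0931) = 0.383
- q = 30%: 0.069 × 0.7 / (0.069 + 0.2793) = 0.139
- q = 50%: 0.069 × 0.5 / (0.069 + 0.4655) = 0.065

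| Uptake q | Dip, absolute (g/L) | Dip, change from baseline (g/L) |
|---|---|---|
| 0% | 18.0 | 5.6 |
| 10% | 18.0 × 0.383 = 6.9 | 5.6 × 0.383 = 2.1 |
| 30% | 18.0 × 0.139 = 2.5 | 5.6 × 0.139 = 0.8 |
| 50% | 18.0 × 0.065 = 1.2 | 5.6 × 0.065 = 0.4 |

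The change-scale result is sensitive to the SD of individual change. With SD 0 it is about 0 at every uptake. With SD 8 it is 10.6, 5.3 and 2.2 g/L at 0, 10 and 30%.

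**3. If haemoglobin really recovers.** A second model assumes baseline mean 142 and SD 11 g/L, within-patient SD 4 or 6, individual response SD 4, lower limit 120 or 125, and linear recovery to zero by Follow-up 6. The true iclepertin mean changes are −3.3 at EOT, −2.2 at Follow-up 2, −1.1 at Follow-up 4 and 0.0 at Follow-up 6. The observed Follow-up 2 value would be
- q = 0: −5.7 to −8.2
- q = 10%: −3.6 to −4.8
- q = 25%: −2.8 to −3.4, roughly level with EOT, so early recovery is hidden
- q = 50%: −2.4 to −2.7, no dip below EOT
- q = 100%: −2.2

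Placebo is affected too: −4.2 to −6.7 at q = 0, against a true −0.3. The two distortions do not cancel, because alert rates differ by arm (about 5–12% against 3–8%). With within-patient SD 4 and lower limit 125, the difference in absolute haemoglobin at Follow-up 2 is 141.3 − 143.2 = −1.9 g/L in all patients. It is 134.4 − 137.8 = −3.4 at 10% uptake and 125.7 − 125.5 = +0.2 at 0%.

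**4. Would a paired change repair it?** In the no-change model, the change from EOT to Follow-up 2 within tested patients is +2.6 g/L at q = 0 and 2.6 × 0.383 = +1.0 at q = 10%. Alerts are selected on the EOT value, so regression to the mean appears as recovery.

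**The case against.** The strongest case on the other side has five parts.

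- **Uptake is unknown.** The bracketed X means discretion, not an alert trigger. If half or more of the patients without an alert are tested, little or nothing is visible. This stands: a reader might infer that the haemoglobin curve will dip and rebound, and the documents support only that it can.
- **Scale.** A reader might set the 18 g/L dip against the 2.8 g/L drug effect and conclude that the artefact is several times larger. That mixes absolute haemoglobin, which carries between-patient and sex differences, with a change from baseline. On the matching scale the central-case dip exceeds 2.8 g/L only at very low uptake. The absolute scale still matters, because SAP 7.8.2 speaks of descriptive statistics for laboratory values.
- **The sample is not made up of alerted patients by rule.** The alert rule covers the haematology panels only, is worded as a recommendation, and allows earlier retesting. Patients who stop early continue scheduled visits, so some of their mandatory samples can fall in days 13–19. Their own Follow-up 2, with eEOT up to 7 days after last dose, can fall on days 13–22 and so partly in the Follow-up 4 row. All this dilutes the selection. For other laboratory parameters no alert rule applies, although protocol 5.2.3 asks that clinically relevant abnormal results be followed.
- **Reversibility.** Protocol 3.2 speaks of unexpected effects, and haemoglobin decrease is expected. Section 3.2 then refers haemoglobin to 5.2.6.4, where alerted patients are followed individually. The sentence is therefore no haemoglobin-specific promise. The follow-up summary is still where recovery after stopping would be read.
- **The display.** No recovery curve is named, no safety hypothesis is tested, N is shown, and the sponsor's laboratory standard is not available here. That limits the consequence. It does not remove the unqualified Follow-up 2 row from the plan.

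**Conclusion.** The point holds as a risk of misleading description. Followed as written, the SAP can produce a Follow-up 2 haemoglobin summary that is biased low by selection, in both arms. The sequence EOT, Follow-up 2, Follow-up 4, Follow-up 6 can then show a false dip and rebound or hide early recovery. The direction follows from the documents. The size does not: it rests on uptake among patients without an alert and on the assumed haemoglobin distribution, so the model figures show a range and are not a forecast. Only haematology is alert-driven, weight and vital signs are unaffected, and nothing inferential depends on the row.

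**What to change.** In SAP Table 6.7: 9, state that the Follow-up 2 row applies to weight and vital signs only. Base the by-visit post-treatment laboratory summaries in 7.8.2 on the scheduled Follow-up 4 and Follow-up 6 samples, identified by nominal visit so that optional samples from early stoppers do not enter the Follow-up 4 row. Present Follow-up 2 laboratory values in a listing labelled as discretionary or alert-triggered.

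Do not replace the row with the paired change from the last on-treatment value, for the reason in step 4 of the working.

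The cost is a short SAP edit and the loss of a partial Day-14 laboratory summary. It needs no new data and does not change who is tested. It should be made before unblinding, because dropping or relabelling a row afterwards would look data-driven.
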